### **EGFR mutations rates in Serbia**

The rate of EGFR mutations in patients with NSCLC in Serbia is currently unknown. Previous studies with gefitinib have shown the incidence of mutations to be around 8% in unselected patients, whereas studies conducted in Asia show mutation rates of 19-60%. As the rate of EGFR mutations amongst NSCLC patients in the Serbia is currently unknown, the health burden and economic implications of treatments directed specifically at patients with this characteristic cannot be accurately assessed.

### **Purpose of the study**

Therefore ,the purpose of the current study is to test the efficacy and safety of the erlotinib as a first-line therapy in patients with NSCLC in locally advanced or metastatic stages (stage IIIB and stage IV) with activating mutations in the tyrosine kinase (TK) domain of the epidermal growth factor receptor (EGFR).

Also, it will be assessed the EGFR mutation rate in Serbia NSCLC population. This will be done by testing Serbia patients with locally advanced or metastatic NSCLC for the EGFR mutations.

Beside this, it will be assesed the impact of erlotinib treatment on quality of life.

The results of this study will help to validate the utility of detecting EGFR mutations for improving treatment selection in this patient population, which will be beneficial.

## **2. OBJECTIVES**

### **2.1 Primary Objectives**

Efficacy of erlotinib (TarcevaTM; 150 mg) on progression-free survival (PFS) in patients with non-small-cell lung cancer (NSCLC) in locally advanced or metastatic stages (stage IIIB and stage IV) who have not received previous chemotherapy for their disease and who present activating mutations in the tyrosine kinase (TK) domain of the epidermal growth factor receptor (EGFR).

### **2.2 Secondary Objectives**

1. Response rate.
2. Safety profile.
3. To assess the incidence of EGFR mutations in NSCLC patients tested in Serbia.

## **3. STUDY DESIGN**

[figure not shown]
### **3.1 Overview of Study Design**

This is a open-label, multi-center Phase IIIb study of erlotinib treatment in patients with locally advanced or metastatic non-small cell lung cancer who present activating mutations in the tyrosine kinase domain of the epidermal growth factor receptor.

The first part of the study is the diagnostic phase which will test patients with advanced or metastatic NSCLC for EGFR mutations. Patients who do not have an EGFR mutation will be excluded from the trial. Patients found to have a tumour with EGFR mutations will then be offered treatment in the treatment phase of the study. The treatment phase is a single arm, open label study using erlotinib as first-line therapy. All enrolled patients into the treatment phase will receive erlotinib 150 mg/day until event. Erlotinib dose will be reduced for toxicities as detailed in Section 6.1.1. Event is defined as progression of disease, death, unacceptable toxicity or withdrawal of consent.

Summary of the study design is shown in Figure 1.

**Figure 1: Summary of study design.**

### 3.1.1 Rationale for Study Design

The purpose of this study is to examine efficacy and safety of erlotinib in first line treatment among patients with locally advanced or metastatic non-small cell lung cancer disease found to have an EGFR exon 19 deletion or exon 21 mutation. The primary efficacy variable will be PFS. Also, since the incidence of EGFR mutations in Serbia is currently unknown, it will be assessed the rate of EGFR mutation in Serbia NSCLC population.

### 3.1.2 Rationale for Dose Selection

The dose of erlotinib to be used in treatment phase will be 150mg/day. No dose escalation of erlotinib is permitted. Erlotinib dose will be reduced for toxicities as detailed in Section 6.1.1. Patients will be treated until progression of disease or unacceptable toxicity.

### 3.1.3 End of Study

The diagnostic phase will end when approximately 300 patients have been tested for EGFR mutations and this phase is expected to last approximately 24 months. The treatment phase is event driven and will end when all eligible patients have experienced progressive disease, death, unacceptable toxicities or withdrawn consent. The overall

duration of the study is expected to be 36 months. The end of the trial will be when the last patient experiences either progressive disease, death, unacceptable toxicities or withdraws consent. The study will end when the last patient has stopped erlotinib therapy and completed their last visit.

### **3.2 Number of Patients / Assignment to Treatment Groups**

A total of approximately 300 patients will be enrolled into the diagnostic phase of this study.

30 patients will be enrolled into the treatment phase of the study.

### **3.3 Centers**

This study will comprise 5 centers in Serbia.

## **4. STUDY POPULATION**

Under no circumstances are patients who enroll in this study permitted to be re-enrolled for a second course of treatment.

### **4.1 Overview**

The target population of this study is patients with histologically or cytologically confirmed locally advanced or metastatic (stage IIIB/IV) NSCLC who have not received previous chemotherapy for their disease (diagnostic phase) and who present activating mutations in the TK domain of the EGFR (treatment phase).

All patients with diagnosed histologically confirmed locally advanced or metastatic (stage IIIB/IV) NSCLC who have not received previous chemotherapy for their disease will be offered screening for EGFR mutations. All patients found to have exon 19 deletion or exon 21 mutation of the EGFR will be offered treatment with erlotinib in the treatment phase of the study. Patients who do not have an EGFR mutation or deletion will be excluded from the study.

### **4.2 Inclusion Criteria**

#### Diagnostic phase

1. Patients able and willing to give written informed consent. Consent must be obtained prior to any study-specific procedure.
2. Histologically or cytologically documented inoperable, locally advanced (stage IIIB with supraclavicular lymph node metastases or malignant pleural or pericardial effusion) or metastatic (stage IV) NSCLC disease
3. Measurable disease must be characterized according to the Response Evaluation Criteria in Solid Tumors (RECIST) criteria.
4. Male or female patients aged  $\geq 18$  years.
5. ECOG performance status 0-2.

6. Life expectancy  $\geq$  12 weeks.

#### Treatment phase

1. Patients must have been proven to have a histologically confirmed EGFR mutation in the diagnostic phase of the study
2. Adequate hematological function: Absolute neutrophil count (ANC)  $\geq 1.5 \times 10^9/L$ , and Platelet count  $\geq 100 \times 10^9/L$ , and Hemoglobin  $\geq 9 \text{ g/dL}$  (may be transfused to maintain or exceed this level).
3. Adequate liver function: Total bilirubin  $< 1.5 \times$  upper limit of normal (ULN), and aspartate aminotransferase (ASAT), alanine aminotransferase (ALAT)  $< 2.5 \times$  ULN in patients without liver metastases;  $< 5 \times$  ULN in patients with liver metastases.
4. Adequate renal function: Serum creatinine  $\leq 1.25 \times$  ULN, Creatinine clearance  $\geq 60 \text{ ml/min}$ .
5. Able to comply with the required protocol and follow-up procedures, including answering the QoL questionnaire and able to receive oral medications.
6. Female patients must be postmenopausal (24 months of amenorrhea), surgically sterile or they must agree to use a physical method of contraception. Male patients must be surgically sterile or agree to use a barrier method of contraception. Women with an intact uterus (unless amenorrhoeic for the last 24 months) must have a negative pregnancy test (urine or serum) within 3 days prior to enrolment into the study. Male and female patients must use effective contraception during the study and for a period of 60 days following the last administration of erlotinib. Acceptable methods of contraception include an established hormonal therapy or intrauterine device for females, and the use of a barrier contraceptive (i.e. diaphragm or condoms) with spermicide.
7. Patients with asymptomatic and stable cerebral metastases receiving medical treatment will be eligible for the study. Those patients may have received radiation therapy for their cerebral metastases before the initiation of systemic treatment for non-small-cell lung cancer also will be eligible.

#### **4.3 Exclusion Criteria**

1. Previous treatment with chemotherapy or therapy against EGFR, either with antibody or small molecule (tyrosine kinase inhibitor) for metastatic disease. The administration of neoadjuvant or adjuvant therapy is allowed as long as it has finalized  $\geq 6$  months before entering the study. Patients can have received radiotherapy as long as the irradiated lesion is not the only target lesion for evaluating response and as long as radiotherapy has been completed before initiating the study treatment (a 2-week period is recommended).
2. Treatment with an investigational drug agent during the 3 weeks before enrollment in the study.
3. History of another neoplasm other than carcinoma in situ of the uterine cervix, basal cell skin carcinoma treated adequately, or prostate carcinoma with a good prognosis

(Gleason ≤ 6) treated radically. History of another neoplasm treated curatively and without evidence of disease in the last 5 years.

4. Patients with symptomatic cerebral metastases.
5. Known hypersensitivity to erlotinib or any of its excipients.
6. Any significant ophthalmologic abnormality, especially severe dry eye syndrome, keratoconjunctivitis sicca, Sjögren's syndrome, severe exposure keratitis or any other disorder likely to increase the risk of corneal epithelial lesions. The use of contact lenses is not recommended during the study. The decision to continue to wear contact lenses should be discussed with the patient's treating oncologist and the ophthalmologist.
7. Coumarins (CoumadinTM; warfarin) use. If the patient requires anti-coagulation therapy, the use of low molecular weight heparin instead of coumarins is recommended where clinically possible.
8. Unstable systemic disease (including active infection, uncontrolled hypertension, unstable angina, congestive heart failure, myocardial infarction within the previous year, serious cardiac arrhythmia requiring medication, hepatic, renal, or metabolic disease).
9. Evidence of any other disease, neurological or metabolic dysfunction, physical examination or laboratory finding giving reasonable suspicion of a disease or condition that contraindicates the use of an investigational drug or puts the patient at high risk for treatment-related complications.
10. Positive urine or serum pregnancy test in women of childbearing potential. Patients (male or female) with reproductive potential not willing to use effective method of contraception. Female patients should not be pregnant or breast-feeding. Oral or injectable contraceptive agents cannot be the sole method of contraception.
11. Patients with pre-existing parenchymal lung disease such as pulmonary fibrosis, lymphangiosis carcinomatosis.
12. Patients with known infection with HIV, HBV, HCV. Testing is not required in the absence of clinical signs and symptoms suggestive of these conditions.
13. Patients assessed by the investigator to be unable or unwilling to comply with the requirements of the protocol.
14. Incapacity to take oral medication or previous surgical procedures that affect absorption and imply the need for intravenous or parenteral feeding.

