#### **Scheduling of tumor assessments**

In this study, assessment of tumor progression during treatment with erlotinib will be performed every 6th week during the study visits and on the End of Study visit (as given in the Schedule of Assessments). Baseline total tumor burden must be assessed within a maximum of 2 weeks before first dose of study drug treatment. Post-baseline assessments are to be performed within +/- 1 week for the 6 weekly assessments. If there is suspicion of disease progression based on clinical or laboratory findings, a tumor assessment should be performed as soon as possible, before the next scheduled evaluation.

If a patient inadvertently misses a prescribed tumor evaluation or a technical error prevents the evaluation, the patient may continue treatment until the next scheduled assessment, unless signs of clinical progression are present.

Tumor response should be confirmed at a minimum of 4 weeks after initial response was noted, or at the next scheduled tumor assessment if it will occur more than 4 weeks after the response was first noted.

For the confirmation of Stable Disease (SD), follow-up measurements must have met the SD criteria at least once after study entry at a minimum interval of 6 weeks.

The diagnosis of disease progression will be made by objective criteria (RECIST criteria) on the target lesion(s), or by documenting, with CT/MRI scans or X-Rays, the presence of newly occurring lesion(s) arising outside the scanned areas of the target lesions.

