### **8.1 Primary and Secondary Study Variables**

#### **8.1.1 Primary Variable**

The primary efficacy variable is progression free survival (PFS). The time to progression is defined as the time from start of treatment to the date of the first documented progression (according to RECIST criteria) or the date of death for any reason in the absence of PD. Patients who have not died or progressed at the time of the final analysis will be censored at the date of last contact.

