###### 1.3. Special considerations regarding lesion measurability

Bone lesions, cystic lesions, and lesions previously treated with local therapy require particular comment:

Bone lesions:.

- Bone scan, PET scan or plain films are not considered adequate imaging techniques to measure bone lesions. However, these techniques can be used to confirm the presence or disappearance of bone lesions.
- Lytic bone lesions or mixed lytic-blastic lesions, with identifiable soft tissue components, that can be evaluated by cross sectional imaging techniques such as CT or MRI can be considered as measurable lesions if the soft tissue component meets the definition of measurability described above.
- Blastic bone lesions are non-measurable.

Cystic lesions:.

- Lesions that meet the criteria for radiographically defined simple cysts should not be considered as malignant lesions (neither measurable nor non-measurable) since they are, by definition, simple cysts.
- „Cystic lesions“ thought to represent cystic metastases can be considered as measurable lesions, if they meet the definition of measurability described above. However, if noncystic lesions are present in the same patient, these are preferred for selection as target lesions.

Lesions with prior local treatment:

- Tumour lesions situated in a previously irradiated area, or in an area subjected to other loco-regional therapy, are usually not considered measurable unless there has been demonstrated progression in the lesion. Study protocols should detail the conditions under which such lesions would be considered measurable.

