#### 3.1. Evaluation of target lesions

**Complete Response (CR):** Disappearance of all target lesions. Any pathological lymph nodes (whether target or non-target) must have reduction in short axis to <10 mm.

**Partial Response (PR):** At least a 30% decrease in the sum of diameters of target lesions, taking as reference the baseline sum diameters.

**Progressive Disease (PD):** At least a 20% increase in the sum of diameters of target lesions, taking as reference the smallest sum on study (this includes the baseline sum if that is the smallest on study). In addition to the relative increase of 20%, the sum must

also demonstrate an absolute increase of at least 5 mm. (Note: the appearance of one or more new lesions is also considered progression).

**Stable Disease (SD):** Neither sufficient shrinkage to qualify for PR nor sufficient increase to qualify for PD, taking as reference the smallest sumdiameterswhile on study.

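### A recently irradiated lesion that has not progressed can be one of several RECIST target lesions, so radiotherapy shrinkage can enter response, disease control and PFS

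*Combined protocol and SAP*

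**What the plan says.** Section 4.3, criterion 1, repeated word for word in the synopsis, sets the only rule in the protocol body on irradiated lesions as targets: "Patients can have received radiotherapy as long as the irradiated lesion is not the only target lesion for evaluating response". The same sentence adds the timing condition that "radiotherapy has been completed before initiating the study treatment (a 2-week period is recommended"). The two weeks are advice; the requirement is only that radiotherapy ends before the first dose.

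Section 5.3.1 adopts RECIST as set out in Appendix 1. Section 1.3 of that appendix says that lesions in a previously irradiated area "are usually not considered measurable unless there has been demonstrated progression in the lesion", and then: "Study protocols should detail the conditions under which such lesions would be considered measurable". No such conditions appear in the body.

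The timing of the baseline scan is given in more than one way. Section 5.3.1 states: "Baseline total tumor burden must be assessed within a maximum of 2 weeks before first dose of study drug treatment". The Schedule of Assessments has a tumor assessment at screening, days −7 to −3, and Section 5.1 lists it at a screening visit within 7 days of starting therapy.

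Partial response is defined in Appendix 1, section 3.1 as "At least a 30% decrease in the sum of diameters of target lesions, taking as reference the baseline sum diameters". Progression in target lesions is "At least a 20% increase in the sum of diameters of target lesions, taking as reference the smallest sum on study", together with an absolute rise of at least 5 mm. These calls feed the primary variable, PFS (Section 8.1.1), and the response and disease control rates (Section 8.1.2). Section 3.2 plans 30 treated patients.

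**The concern.** Criterion 1 implies that an irradiated lesion is acceptable as a target when another target is present. It does not ask whether the lesion has progressed since radiotherapy, which is the condition Appendix 1 attaches.

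If the lesion shrinks after the baseline scan because of radiotherapy, that shrinkage goes into the sum and is indistinguishable from a drug effect. It can produce a partial response by itself, or cancel growth in another target so that an assessment reads as stable disease. The treatment phase has one arm, so no comparison group shares the error. The cohort is small, so a few misclassified patients are visible in the reported rates.

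The point concerns lesions irradiated before study treatment and selected as targets at baseline. Radiotherapy given on study, which Section 4.4 allows, is a separate matter.

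**Working it through.** The plan has no figure of its own on this point to reproduce. The check has three parts: the timing rules, the RECIST arithmetic, and the effect of one patient. Lesion sizes are assumed for illustration, because the documents give none.

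**1. Can radiation shrinkage fall after baseline?**

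- Radiotherapy ending on day −1 with a scan on day −14 complies with Section 4.3 and Section 5.3.1.
- Radiotherapy ending on day −1 with a scan on day −7 complies with Section 4.3, Section 5.1 and the Schedule of Assessments.
- If the recommended two weeks are kept and the scan is within 7 days, the scan falls at least 14 − 7 = 7 days after radiotherapy. Only shrinkage continuing beyond that point would matter. The documents do not say how long it continues.

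So every stated scan window allows a baseline scan before radiotherapy is finished.

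**2. False partial response.** Let the irradiated lesion be a share s of the baseline sum and shrink by a fraction x, with the other targets unchanged. The sum falls by s·x, so a partial response needs s·x ≥ 0.30, or x ≥ 0.30/s.

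| Share s | Shrinkage needed, 0.30/s |
|---|---|
| 30% | 100% |
| 40% | 75% |
| 50% | 60% |
| 60% | 50% |
| 70% | 43% |

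Example: 50 + 50 mm becomes 20 + 50 = 70 mm, a fall of 30%.

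**3. Effect on progression.** Start with two targets of 40 mm, sum 80 mm.

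- *Offset.* At one scan the irradiated lesion is 24 mm and the other 56 mm. The sum is 24 + 56 = 80 mm, a change of 0%, so there is no target progression. The non-irradiated lesion alone went from 40 to 56 mm (+40%, +16 mm), which meets the criterion. This can happen at the first post-baseline scan, where the smallest earlier sum is the baseline itself.
- *Same lesions, shrinkage seen first.* One scan shows 24 + 40 = 64 mm, which becomes the reference. The next shows 24 + 56 = 80 mm. The rise is 16/64 = 25% and 16 mm: progression.
- *Lowered reference.* From 24 + 40 = 64 mm the irradiated lesion regrows to 37 mm and the other stays at 40 mm. The sum is 77 mm, a rise of 13/64 = 20.3% and 13 mm: progression is called, although the non-irradiated lesion has not changed.

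The distortion of PFS therefore depends on the order of events and can go either way.

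**4. Effect per patient.** One false responder among 30 moves the response rate by 1/30 = 3.3 points; three move it by 3/30 = 10 points, for example from 21/30 = 70% to 24/30 = 80%.

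**The case against.** The best defence is that criterion 1 is an eligibility rule, not a lesion-selection rule. Section 5.3.1 applies Appendix 1, under which targets are chosen from measurable lesions and an irradiated lesion usually is not measurable unless it has progressed. Criterion 1 would then be an additional safeguard: even a qualifying irradiated lesion may not stand alone. This reading is possible, so a reader should not infer a flat contradiction. It is not secure, because the appendix says usually and passes the decision to the protocol, and the only body text on the subject implies that an irradiated lesion can be a target.

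A second objection is that timing is less exposed than the two-week window suggests, since other sections put the scan within 7 days. That narrows the risk without removing it, because the gap after radiotherapy is not mandatory.

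Third, a reader might infer that every endpoint, PFS included, is biased upward. The documents do not support that. Progression is measured from the smallest sum on study, so radiation shrinkage can also bring it forward, as shown above. New lesions, unequivocal non-target progression and death still count as events whatever happens to the target sum.

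Fourth, few patients may be involved. A false responder must be a patient who does not respond to erlotinib and whose irradiated lesion is a large part of the sum, with shrinkage lasting at least 4 weeks. Section 1.2 cites a response of 70–90% in this genotype, which would leave 10–30% of 30, or 3 to 9 non-responders; only some of these would have had recent radiotherapy. This stands as a limit on size. The 4-week confirmation does not remove the problem: Appendix 1, section 4.6.1 presents confirmation as protection against measurement error, and sustained shrinkage from another cause passes it.

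**Conclusion.** The gap is real and worth closing. As written, a recently irradiated lesion without progression can be one of several targets, and the conditions that Appendix 1 asks the protocol to state are missing. Shrinkage from radiotherapy *can* then count towards response and disease control; it is not established that it *will*. For those two rates the risk is upward, at 3.3 points of response rate per false responder in 30 patients. For PFS the direction is open.

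This rests on two assumptions: that some patients receive radiotherapy shortly before the first dose, and that part of the shrinkage follows the baseline scan. The documents do not give the number of such patients, so the total bias cannot be calculated; 1/30 is the effect of one patient, not an estimate of the bias. The case for the change is that it is cheap and comes from the protocol's own appendix.

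**What to change.** In Section 4.3, the synopsis and the CRF target-lesion instructions, replace the clause on irradiated target lesions with:

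*A previously irradiated lesion may be selected as a target lesion only if progression in that lesion has been demonstrated since radiotherapy; otherwise it is followed as non-target. At least one non-irradiated measurable lesion must be available as a target.*

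This governs the choice of lesions for measurement only and changes no radiotherapy or treatment rule.

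The cost is small but not nil:

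- Some patients will have one lesion fewer in the sum.
- Regrowth of an irradiated lesion followed as non-target is judged by the stricter non-target standard in Appendix 1, section 3.4, so some progression calls may come later.
- Eligibility is slightly affected. Read literally, the present wording admits a patient with two targets that were both irradiated, since neither is the only one. The rare patient whose measurable lesions were all irradiated would no longer qualify.
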